### 6.1.2.3 Weeks 6 to 24 (Every 2 weeks, $\pm 4$ days)

- Laboratory tests (must be performed prior to dosing):
  - Weeks 8, 12, 20: CBC with WBC differential
  - Week 6 followed by every visit where no CBC is collected; Hb only.
  - Weeks 8, 12, 20: Serum chemistry
  - Weeks 6, 16: LFTs and CPK
  - Weeks 8, 12, 24: Lipid panel (fasting whenever possible).
  - Weeks 8, 12, 20: Serum iron, ferritin, TIBC, TSAT.
  - Weeks 8, 12, 20: CHr
  - Week 12: HbA1c
  - Weeks 8, 20: Reticulocyte count
  - Weeks 12, 20: Special laboratory analytes

- Weeks 12, 20: Archival serum/plasma samples (optional donation, separate consent form)
- HemoCue®/CritLine® assessment
- Weeks 12, 24: Serum hCG pregnancy test for women of childbearing potential (for definition, see [Section 3.6.6](#))
- 
- Week 24 followed by every 12 weeks: Targeted physical exam (eg, respiratory and cardiovascular system)
- Week 24 followed by every 24 weeks: 12-lead ECG, weight (HD subjects: dry weight)
- Dose adjustment review every 4 weeks (except in the event of excessive hematopoiesis or dose frequency conversion). Refer to [Section 3.5.2](#), and [Appendix 2](#).
- All visit weeks: BP and HR
- Week 12 HRQoL questionnaires (SF-36, FACT-An, and EQ-5D-5L)
- Adverse event recording
- Concomitant medication recording
- Procedures and nondrug therapy recording
- Dispense study drug

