5.4 ADDITIONAL DATA HANDLING RULES AND PRESENTATION SPECIFICATIONS

The following general guidelines will apply to all statistical analyses and data presentations:

- Baseline is defined as the last available value obtained prior to the first dose of study drug, unless otherwise specified in this SAP.
- Hb baseline is defined as the mean of the at least last three available values obtained prior to the first dose.
- Baselines for reticulocyte count, reticulocyte hemoglobin content (CHr), hepcidin, serum iron parameters (transferring, TIBC, TSAT, Ferritin, sTfR, and iron), lipids, blood pressures and heart rate are defined as the mean of values obtained within 6 weeks prior to the first dose.
- Randomization stratification factors and enrollment protocol version derived from actual data (not the ones from the randomization system) will be used in all applicable analysis models.

The stratification factors to be used in efficacy analyses are:

1. Us vs Ex-US Screening Hb values (≤ 8 g/dL vs. > 8 g/dL) (other than Hb related endpoints)
2. Cardiovascular/cerebrovascular/thromboembolic medical history (Yes vs. No)
3. Geographic Region
4. The original protocol and amended protocols

- Unscheduled visits within an allowable window will be grouped into the closest scheduled visits based on the visit window specified in Appendix 1. For subjects who have more than one measurement at a certain scheduled visit, the last measurements

will be used, with the exception of CPK, WBC, liver function tests (i.e., ALT, AST, GGT, ALP, and total bilirubin), in which the maximum measurement will be used.

- By default, US conventional units will be used for laboratory value presentations. A set of lab summary tables in SI units will also be provided based on TLF index.
- Age is calculated as of date that the informed consent form was signed.
 - age = INTCK('YEAR', Birth date, date of Informed Consent, 'C') where INTCK is a SAS function.
- Duration of treatment or days in treatment is calculated as: last dose date – first dose date +1
- Body weight, height and temperatures will be converted using the following formula:
 - kg = lb/2.2
 - cm = 2.54 x in
 - C° = (5/9) x (F° – 32)
- The mean, standard deviation and median will be presented with adding one more decimal to raw data with rounding off. The minimum and maximum will be presented with the same number of decimals as in the raw data.

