11.2 ANALYSIS OF SECONDARY ENDPOINTS

The secondary endpoints are for both U.S. and Ex-U.S. submission unless otherwise specified. Once the primary hypothesis has been rejected for the primary endpoint, the secondary endpoints in the order that was specified in section 4.3 will be tested using a fixed sequence testing procedure, in order to maintain the overall two-sided type I error of 0.05. If p-value from a test is < 0.05, the claim of superiority or non-inferiority will be considered successful and the test will progress to the next comparison in sequence as follows.

Table 5 Key Secondary Endpoints Fixed Sequence Testing Procedure

Test	Variable	Comparison
1	Proportion of subjects who achieve an Hb response at two consecutive visits during the first 24 weeks of treatment, (U.S.) or the mean Hb change from baseline to the average level during the Evaluation Period, defined as Week 28 until Week 52 for Ex-U.S..	Non-inferiority of roxadustat versus EPO. The non-inferiority margin for the difference of responder analysis between groups is 0.15 The non-inferiority margin for the difference of average of Change in Hb values between groups is - 0.75 g/dL.
2	LDL cholesterol change from BL to the average of weeks 12 to 24.	Superiority of roxadustat versus EPO
3	Mean change from baseline in Hb levels between Weeks 18 to 24 in patients whose baseline CRP > ULN:	The non-inferiority with margin of - 0.75 of roxadustat versus EPO
4	Monthly IV iron (mg) use per subject during weeks 28 to 52.	Superiority of roxadustat versus EPO
45	Time to first RBC transfusion during the treatment.	Non-inferiority of roxadustat versus EPO with Non-inferiority margin of 1.8
5	Change from BL to the average MAP of weeks 8 to 12	Superiority of roxadustat versus EPO
6	Time to first exacerbation of hypertension (defined as [systolic BP \geq 170 mmHg AND systolic BP increase from BL \geq 20 mmHg] or [diastolic BP \geq 110 mmHg AND diastolic BP increase from BL \geq 15 mmHg]) during weeks 28 to 52	Superiority of roxadustat versus EPO & Non-inferiority with margin of 1.8

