16.2 APPENDIX 2: DATA HANDLING CONVENTIONS

16.2.1 VISIT TIME WINDOW

Table 9 below presents the visits assigned for efficacy and safety analyses corresponding to the range of treatment days (window) during which an actual visit may have occurred.

Table 9. Analysis Visit Windows

Derived Visit	Scheduled Visit Day ^a	Window
Baseline, Week 0	Day 1	Days \leq 1
Week 1	Day 7*(Week #)+1	[Day 2, 10]
Weeks 2-3	Day 7*(Week #)+1	Days [Scheduled Day \pm 3]
Week 4	Day 7*(Week #)+1	[Scheduled Day -3, Scheduled Day +6]
Weeks 4-22	Day 7*(Week #)+1	[Scheduled Day -7, Scheduled Day +6]
Week 24	Day 7*(Week #)+1	[Scheduled Day -7, Scheduled Day +13]
Week 24 to xx	Day 7*(Week#)+1	[Scheduled Day -14, Scheduled Day +13]
ET	Earlier Termination, Match to a closest scheduled visit in protocol if patient had not been off drug for more than 7 days.	
EoT	Last assessment between Day 2 and EOT visit day, match to a closest scheduled visit in protocol if patient had not been off drug for more than 7 days.	
EoS (FU-4Wk)	Final visit for the Study 15 – 31 days after the last dose (excluding long term follow-up for early termination)	

^a: Relative to the first study medication date. For example, Day 1 = the first dose date of study medication.

Analysis Visit windows, as depicted in Table 10 below, will be used for the quality of life efficacy study assessments:

Table 10: Analysis Visit Windows for QoL

CRF Visit	Target Day ^a	Analysis Visit Windows Actual Assessment Day	Analysis Visit
Day 1	Day 1	Day 1	Baseline
Week 12	Day 7 * (Week #) + 1	[Target Day -14, Target Day + 27]	Week 12
Week 36	Day 7 * (Week #) + 1	[Target Day – 28, Target Day +27]	Week 36
Week 52	Day 7 * (Week #) + 1	\geq Target Day – 56, Target day + 83	Week 52
EOT Visit		Last assessment between Day 2 and EOT visit day, remapped to the closest next scheduled visit for HRQoL collection.	Week 12, 36, 52 and > 1 year

^a: Relative to Day 1 (first dose date of study medication)

Table 11. Analysis Visit Windows for Lipid Panel

Derived Visit	Scheduled Visit Day ^a	Window
Baseline, Week 0	Day 1	Days 1
Week 4	Day 7*(Week #)+1	[Day 2, 42]
Week 8	Day 7*(Week #)+1	[Scheduled Day -14, Scheduled Day +13]
Weeks 12	Day 7*(Week #)+1	[Scheduled Day -14, Scheduled Day +27]
Week 24	Day 7*(Week #)+1	[Scheduled Day -28, Scheduled Day +27]
Weeks 32-40	Day 7*(Week #)+1	[Scheduled Day -28, Scheduled Day +27]
Week 48	Day 7*(Week #)+1	[Scheduled Day -28, Scheduled Day +41]
Week 60	Day 7*(Week #)+1	[Scheduled Day -42, Scheduled Day +83]

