Week 84 to xx	Day 7*(Week#)+1	[Scheduled Day -84, Scheduled Day 83]
EoT	Last assessment between Day 2 and EOT visit day, match to a closest scheduled visit in protocol if patient had not been off drug for more than 7 days	

^a: Relative to Day 1 (first dose date of study medication)

Visit Day is calculated by (visit date - date of first study medication + 1). If a patient has ≥ 2 actual visits within the same window, the last visit with non-missing value will be used for analysis.

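### SAP Table 11 gives Days 113–140 no lipid visit, so a late or unscheduled LDL value there has no defined place in the Week 12–24 endpoint

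*SAP*

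**What the plan says.** **Windows.** SAP section 16.2.1, Table 11, defines the derived visits for the lipid panel. The scheduled day is 7 × week number + 1, counted from the first dose as Day 1. The Week 12 row reads "Scheduled Day -14, Scheduled Day +27" and the Week 24 row reads "Scheduled Day -28, Scheduled Day +27". No lipid visit is listed between them.

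**Values that are off schedule.** SAP section 5.4 states: "Unscheduled visits within an allowable window will be grouped into the closest scheduled visits based on the visit window specified in Appendix 1". (Table 11 itself stands in Appendix 2.) Neither section says what happens to a value that lies in no window. Where a window holds two or more visits, section 16.2.1 says "the last visit with non-missing value will be used for analysis", and section 5.4 has the same default. The end-of-treatment row of Table 11 has its own rule: "match to a closest scheduled visit in protocol if patient had not been off drug for more than 7 days".

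**Planned draws.** Protocol section 6.1.2.3 schedules "Weeks 8, 12, 24: Lipid panel (fasting whenever possible", with visits every 2 weeks and a tolerance of ±4 days. No panel is planned between Weeks 12 and 24.

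**Use.** Test 2 in SAP Table 5 is "LDL cholesterol change from BL to the average of weeks 12 to 24". Section 11.2.1.2 estimates it from a mixed model on data up to Week 52, with a contrast over the derived visits from Week 12 to Week 24. The proportion of subjects with LDL below 100 mg/dL over the same period (sections 4.4 and 11.3.5) uses the same visits.

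**The concern.** Weeks 12 and 24 are the only derived lipid visits inside the endpoint period. A 28-day stretch between them, which includes the midpoint of the period, is assigned to neither.

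The exposed case is a subject whose Week 12 panel is missed and made up at about Week 16 or 18, or who has an unscheduled panel then. That LDL value lies inside the period the endpoint describes but has no derived visit. The subject would then have one of the two values that define the endpoint instead of both.

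Because no rule is written for such values, someone has to decide on them during programming. The study is open-label, and protocol section 8.4.5 wants the SAP settled before substantial data accumulate for that reason. The rule should be on paper first.

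**Working it through.** **Inputs.** Scheduled day = 7 × week + 1; offsets from SAP Table 11; visit tolerance ±4 days from protocol section 6.1.2.3.

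**Step 1: every row of Table 11 in study days.**

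| Lipid visit | Scheduled day | Offsets | Days covered | Unassigned days before next row |
|---|---|---|---|---|
| Week 4 | 29 | fixed | 2–42 | 0 |
| Week 8 | 57 | −14/+13 | 43–70 | 0 |
| Week 12 | 85 | −14/+27 | 71–112 | **28 (113–140)** |
| Week 24 | 169 | −28/+27 | 141–196 | 0 |
| Week 32 | 225 | −28/+27 | 197–252 | 0 |
| Week 40 | 281 | −28/+27 | 253–308 | 0 |
| Week 48 | 337 | −28/+41 | 309–378 | 0 |
| Week 60 | 421 | −42/+83 | 379–504 | 0 |
| Week 84 | 589 | −84/+83 | 505–672 | – |

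Gap: 141 − 112 − 1 = 28 days. As a share of the calendar from Day 85 to Day 169 (85 days), 28/85 = 33%. This counts days, not measurements.

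**Step 2: is the gap deliberate?** In the seven other pairs, the later window starts exactly midway between the two scheduled days. For example, (337 + 421)/2 = 379, the first day of Week 60. Week 48 to Week 60 is a 12-week step, joined by +41 and −42. Week 12 to Week 24 is also a 12-week step, but uses +27 and −28. Its midpoint is (85 + 169)/2 = 127, so the table's own pattern would give Week 12 an upper offset of 126 − 85 = +41 and Week 24 a lower offset of 127 − 169 = −42.

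**Step 3: which draws can land in the gap?**
- Planned Week 12 draw, 85 ± 4: Days 81–89, covered.
- Planned Week 24 draw, 169 ± 4: Days 165–173, covered.
- Catch-up at Week 14, 99 ± 4: Days 95–103, covered as Week 12.
- Catch-up at Week 16, 113 ± 4: Days 109–117. Days 109–112 are covered; Days 113–117 are not.
- Panel at Week 18, 127 ± 4: Days 123–131, none covered.
- Panel at Week 20, 141 ± 4: Days 137–145. Days 137–140 are not covered; Days 141–145 count as Week 24.

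So a Week 12 draw must be at least 113 − 85 = 28 days late, or a Week 24 draw at least 169 − 140 = 29 days early.

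**Step 4: windows after the change.** Week 12 at −14/+41 is Days 71–126 and Week 24 at −42/+27 is Days 127–196, so no day is unassigned. The last-value rule then matters: with an on-time draw on Day 85 and an unscheduled one on Day 120, it would pick Day 120. Choosing the value closest to Day 85 (distance 0 against 35) keeps the on-time draw, while a Day 120 catch-up with no other value is still used.

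**The case against.** The strongest reply is that the gap touches no planned data. Every on-schedule lipid draw and every Week 14 catch-up is covered, and end-of-treatment values are matched to the closest scheduled visit. A subject without a Week 12 value stays in the mixed model through the other derived visits up to Week 52. The windows are the same in both arms, and nothing in the documents shows a bias. All of this stands and keeps the point small.

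It can also be said that gaps occur elsewhere. Table 10 (quality of life) uses the same Week 12 limits and leaves Days 113–224 and 281–308 unassigned. That shows contiguity is not a general rule of this SAP. It does not explain why Table 11 meets at the midpoint everywhere except here.

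Widening the windows alone could do harm through the last-value rule. That is correct, and the fix has to deal with it.

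A reader might infer more than the documents support:
- *That the SAP discards LDL values from mid-period.* It does not say so. Exclusion is the natural reading of having no window together with section 5.4. One could also fall back on the general windows of Table 9, which would place these days at Weeks 16, 18 or 20, although Table 11 has no such lipid visits. Strictly, the handling is unspecified.
- *That using values from outside Weeks 12–24 is a second error.* The two windows do accept Days 71–84 and 170–196, but that is ordinary windowing around a target day. The protocol's own tolerance already admits Days 81–84 and 170–173.
- *That the second step of the testing sequence is in danger.* LDL is second only in Table 5. The text above that table points to the order in section 4.3, where time to first Hb response and exposure time with Hb of at least 10 g/dL come before it. The same five endpoints follow LDL in both lists, but no change in the LDL test result has been shown.

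**Conclusion.** The point holds as a minor defect. Table 11 has one hole, Days 113–140, and the table's own construction indicates that it is a mistake in two limits. A late catch-up or unscheduled LDL value in those 28 days has no derived visit and would most naturally be left out of the Week 12–24 endpoint.

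The number of values affected cannot be derived, because the documents give no rate of very late or unscheduled lipid panels. It is probably small. For a subject who is affected, the loss is one of the two values that define the endpoint.

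This rests on two readings: that section 5.4 leaves a value outside every window unassigned, and that the end-of-treatment rule means the closest scheduled lipid visit. It does not support a claim that planned endpoint data are lost or that the LDL conclusion would change.

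**What to change.** - In Table 11, set Week 12 to −14/+41 (Days 71–126) and Week 24 to −42/+27 (Days 127–196). This follows the limits already used between Weeks 48 and 60.
- State that when a lipid window holds more than one value, the one closest to the scheduled day is used, with the later value if two are equally close. Name this as an exception to the last-value rule in both section 16.2.1 and section 5.4.
- State that an end-of-treatment value on Day 127, which is 42 days from both scheduled days, goes to Week 24, as the new window does.

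The cost is two table cells and a few sentences, with no new data collection. The window change moves no value that already has a visit. The closest-value rule can change which value is used where a lipid window already holds several (for example Days 85 and 105), so it should be recorded as a change and made before LDL is summarised by arm.

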16.2.2 Repeated or Unscheduled Assessments of Safety Parameters

If a patient has repeated assessments prior to the start of study medication, then the results from the final assessment made prior to the start of study medication will be used as baseline. If end of study assessments are repeated or unscheduled, the last post-baseline assessment will be used as the end of study assessment for generating summary statistics. However, all post-baseline assessments will be used for PCS value determination and all assessments will be presented in the data listings.

16.2.3 Missing Date of Study Medication

When the last date of study medication during the study treatment phase is missing, all efforts should be made to obtain the date from the investigator. If it is still missing after all efforts, then the last dispensation visit date during the treatment period will be used in the calculation of treatment duration.

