9 STUDY MEDICATION

9.1 EXTENT OF EXPOSURE

Exposure to study medication will be summarized by treatment group in terms of treatment duration in weeks, which is calculated using the following formula: (the date of last medication taken - the date of first dose taken +1)/7.

Total weekly study drug exposure is defined as the total prescribed dose (in mg and mg/kg for Roxadustat and IU and IU/kg for EPO) of study drug administered within the week (windowed by 7-day period from Day 1).

Duration of exposure, weekly exposure and total study drug exposure will be tabulated by treatment group for the safety population.

Per administration amount and administration frequency will also be tabulated by treatment group for the safety population and PPS population.

Patient-Exposure-Year (PEY) is defined as (Last Dose Date – First Dose Date + 1)/365.25.

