11 EFFICACY ANALYSES

Efficacy analysis will be conducted on the ITT and FAS for US (FDA) submission and analysis for non-inferiority on the PPS population and analysis for superiority on FAS population for EU regulatory submission.

The **Efficacy Emergent Period** is defined as the evaluation period from the Analysis date of first dose intake up to 7 days after the Last Dose of study drug or EOT Visit, whichever occurs first. This period will be used as reference period for the time to event analyses related to efficacy endpoints, unless specified otherwise.

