12.1.1 Proportion of Subjects with TEAE

An AE (classified by preferred term) started during the treatment period will be considered a treatment-emergent adverse event (TEAE) if it was not present prior to the first dose of study medication, or it was present prior to the first dose of study medication but increased in severity during the treatment period up to 7 days after last dose of study drug or until the administration of another anemia drug (other than the randomized treatment). An AE that occurs more than 7 days after the last dose of study medication or after the administration of another anemia drug (other than the randomized treatment) will not be counted as a TEAE.

The number and percentage of subjects reporting TEAEs in each treatment group will be tabulated separately by system organ class and preferred term; by system organ class, preferred term, and severity; and by system organ class, preferred term, and relationship to study medication. If more than one event occurs with the same preferred term for the same patient, the patient will be counted only once for that preferred term using the most severe and most related occurrence for the summarization by severity and by relationship to the study medication.

The distribution of TEAEs by severity and relationship to study medication will be summarized by treatment group.

The incidence of common ($\geq 5\%$ of subjects in any treatment group) TEAEs, treatment-emergent serious AEs (TESAE), and AEs leading to discontinuation of study medication will be summarized by preferred term and treatment group, sorted in decreasing overall (across treatments) frequency. In addition, the incidence of death and fatal SAEs (i.e., events that caused death) and incidence rate per PEY will be summarized separately by treatment group and preferred term.

Listings will be presented of subjects with serious adverse events (SAEs), subjects with adverse events leading to discontinuation, and subjects who died.

Temporal profile of TEAEs of special interest may also be plotted by treatment group showing the subjects in the y-axis and time to these TEAEs in the x-axis (Appendix 8).

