16.2.7 Missing Date Information for Prior or Concomitant Medications

For prior or concomitant medications, including rescue medications, incomplete (i.e., partial missing) start date and/or stop date will be imputed. When the start date and the stop date are both incomplete for a patient, impute the start date first.

- **Incomplete Start Date**

The following rules will be applied to impute the missing numerical fields. If the stop date is complete and the imputed start date is after the stop date, then the start date will be imputed using the stop date.

Missing day and month

If the year of the incomplete start date is the same as the year of the first dose date of study medication, then the day and month of the first dose date will be assigned to the missing fields.

If the year of the incomplete start date is not the same as the year of the first dose date of study medication, then January 1 will be assigned to the missing fields.

Missing month only

Treat day as missing and replace both month and day according to the above procedure.

Missing day only

If the month and year of the incomplete start date are the same as the month and year of the first dose date of study medication, then the day of the first dose date will be assigned to the missing day.

If the month and year of the incomplete start date are the same as the first dose date of study medication, then the first day of the month will be assigned to the missing day.

- **Incomplete Stop Date**

The following rules will be applied to impute the missing numerical fields, if needed. If the last dose date of study medication is missing, impute it with the last visit date. If the imputed stop date is before the start date (imputed or non-imputed start date), then the imputed stop date will be equal to the start date.

Missing day and month

If the year of the incomplete stop date is the same as the year of the last dose date of study medication, then the day and month of the last dose date will be assigned to the missing fields.

If the year of the incomplete stop date is not the same as the year of the last dose date of study medication, then December 31 will be assigned to the missing fields.

Missing month only

Treat day as missing and replace both month and day according to the above procedure.

Missing day only

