16.2.8 Missing Date Imputation for last dose date

Imputed last dose date = earliest date of (last drug dispense date + number of days of drug dispensed, date of death, date of EOT/EOS visit, and other dates as appropriate).

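### SAP 16.2.3 and 16.2.8 impute a missing last-dose date differently, so exposure and the event windows can rest on different dates for the same subject

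*SAP*

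**What the plan says.** Three places in SAP Appendix 2 deal with a missing date of last study medication.

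- **16.2.3** first requires every effort to obtain the date from the investigator. If that fails, "then the last dispensation visit date during the treatment period will be used in the calculation of treatment duration".
- **16.2.8**, headed as the imputation of the last dose date, states: "Imputed last dose date = earliest date of (last drug dispense date + number of days of drug dispensed, date of death". The list continues with the EOT/EOS visit date and ends with an open category of other dates that is not defined.
- **16.2.7**, within the rules for incomplete stop dates of prior, concomitant and rescue medications, states: "If the last dose date of study medication is missing, impute it with the last visit date".

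None of the three refers to another, and no order of precedence is given.

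The date is used widely. SAP 5.4 states "Duration of treatment or days in treatment is calculated as: last dose date", minus the first dose date, plus one. SAP 9.1 states "Patient-Exposure-Year (PEY) is defined as (Last Dose Date", minus the first dose date, plus one, over 365.25. The Efficacy Emergent Period in SAP 11 runs "up to 7 days after the Last Dose of study drug or EOT Visit, whichever occurs first". SAP 12.1.1 removes from the TEAE count "An AE that occurs more than 7 days after the last dose of study medication". SAP 11.3.2 accepts admissions up to 7 days after last medication. SAP 11.3.4.1 ends time at risk for untransfused subjects on that date. SAP Table 9 uses days off drug to decide whether an ET/EOT value is mapped to a scheduled visit.

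**The concern.** Sections 16.2.3 and 16.2.8 are two instructions for one variable. Section 16.2.3 speaks of treatment duration, but duration and PEY are simple functions of the last-dose date, which is what 16.2.8 imputes. A programmer following the SAP cannot satisfy both.

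The 16.2.3 value also has a direction. It closes exposure on the day the last supply was handed out, as if none of that supply was used afterwards. Every date that 16.2.8 names falls on or after the last dispensing, so, leaving aside its undefined other dates, 16.2.3 can never give the later date.

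Rates per PEY are at stake. SAP 12.1.1 says "the incidence of death and fatal SAEs (i.e., events that caused death) and incidence rate per PEY will be summarized separately by treatment group". SAP 11.3.2 also reports hospital days per PEY. If event windows follow one rule and exposure the other, numerator and denominator come from different dates. The trial is open label, and protocol 8.4.5 wants the SAP settled early to avoid bias, so a choice between rules should not be left to programming.

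**Working it through.** The plan gives no figure on this point to reproduce. The check applies the rules to the same hypothetical subjects.

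**Inputs**
- Study day = 7 × week + 1 (SAP Table 9), so Week 28 is Day 197 and Week 12 is Day 85.
- First dose is Day 1, so duration equals the last-dose day, and PEY = last-dose day / 365.25 (SAP 5.4, 9.1).
- Visits at which drug is dispensed are two-weekly in Weeks 6 to 24 and four-weekly from Week 28 (protocol 6.1.2.3, 6.1.2.4). Dispensing is also two-weekly in Weeks 2 to 4 (6.1.2.2). *Assumption:* the supply equals the visit interval, 14 or 28 days. The documents state no dispensed quantity.
- Event windows close 7 days after last dose (SAP 11, 11.3.2, 12.1.1). The Efficacy Emergent Period is also capped by the EOT visit.

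**Step 1: exposure, subject with no earlier cap.** The last dispensing is Day 197 with a 28-day supply.
- 16.2.3: Day 197.
- 16.2.8: 197 + 28 = Day 225.
- Difference: 28 / 365.25 = 0.077 PEY. In the two-weekly phase it is 14 / 365.25 = 0.038 PEY.

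**Step 2: exposure, subject who dies.** The last dispensing is Day 197 and death is on Day 217.
- 16.2.3: Day 197, PEY = 197 / 365.25 = 0.539.
- 16.2.8: min(225, 217) = Day 217, PEY = 217 / 365.25 = 0.594.

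**Step 3: mixed dates.** Each rule is now kept to its stated purpose: 16.2.3 for duration and PEY, 16.2.8 for event windows. For the subject in Step 2, the window closes on Day 217 + 7 = 224, so a fatal event with onset on Day 217 is counted. Exposure stops on Day 197. The event falls 20 days after the end of the exposure that forms its denominator, and 20 / 217 = 9.2% of that subject's 16.2.8 exposure is lost. For affected subjects this raises the rate.

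**Step 4: conditional effect on event status.** This applies only if 16.2.3 were also carried into the event windows, which the SAP neither instructs nor excludes.

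| Case | 16.2.3 window ends | 16.2.8 window ends | Event |
|---|---|---|---|
| Dispensed Day 197, 28 days, death Day 217 | 197 + 7 = 204 | 217 + 7 = 224 | out / in |
| Dispensed Day 85, 14 days, death Day 97 | 85 + 7 = 92 | 97 + 7 = 104 | out / in |

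In general, an event d days after the last dispensing changes status when 7 < d ≤ supply + 7. That is days 8 to 35 for a 28-day supply and days 8 to 21 for a 14-day supply, if no earlier EOT/EOS visit or other cap applies.

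**Step 5: reach.** Untransfused subjects are censored at the last study medication date (SAP 11.3.4.1). Time to first RBC transfusion is in the fixed testing sequence with a non-inferiority margin of 1.8 (SAP Table 5), so the date reaches a tested secondary endpoint. The US primary endpoint (ITT, Weeks 28 to 52) depends on it only through ET/EOT visit mapping.

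**The case against.** The strongest reply is scope. Section 16.2.3 confines itself to treatment duration, and the sentence in 16.2.7 belongs to medication stop dates. Only 16.2.8 is a general last-dose rule. SAP 11.3.4 refers to an Analysis Date of Last Dose, which suggests one derived variable, with 16.2.8 as its natural source. This largely stands for the event windows. It does not remove the conflict over duration and PEY, and it leads directly to the mixed dates in Step 3.

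Four stronger readings are tempting, and the documents do not support them.

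- *The same death or admission is counted or dropped.* This needs 16.2.3 or 16.2.7 to be carried beyond its stated use. SAP 12.1.1 summarises deaths separately without expressly applying the 7-day window, and lists the subjects who died. Subjects who stop drug are followed for vital status until study closure, unless they withdraw consent (protocol 6.1.2.6). Adjudicated events belong to a pooled SAP that is not available here.
- *Three rival dates exist for every use.* The last-visit value of 16.2.7 is given only for completing medication stop dates.
- *The effect falls mainly on roxadustat, or on subjects who die or are lost.* Roxadustat is self-administered and in-centre hemodialysis epoetin is given by trained personnel (protocol 5.3). Home-hemodialysis and peritoneal dialysis epoetin may be given by the subject or a caregiver. The documents contain no data on missing dates by arm or by reason.
- *EOS should be removed from 16.2.8 because it follows treatment.* In an earliest-of rule it acts only as an upper cap. With no EOT visit and an EOS visit 20 days after a 28-day dispensing, 16.2.8 gives day 20. Without EOS, and with no other date, it gives day 28, eight days after the final visit.

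The query step in 16.2.3 also stands: only dates still missing after it are affected.

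**Conclusion.** The inconsistency is real and should be corrected, but its demonstrated reach is narrow. Sections 16.2.3 and 16.2.8 conflict on treatment duration and PEY, with no precedence stated, and 16.2.7 adds a third value for a limited purpose. Per affected subject, the 16.2.3 value falls short by up to the length of the last supply. The 14- or 28-day size rests on the assumption that supply equals the visit interval. Mixed dates in rates per PEY follow if each rule is kept to its stated purpose. A change in TEAE or hospitalization status is conditional on 16.2.3 being extended to those windows. The total effect cannot be sized, because the number of residual missing dates is not in the documents. Nothing here shows a material effect on the US primary result.

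**What to change.** Make 16.2.8 the only rule for a missing last-dose date. Keep the query requirement in 16.2.3, but replace its imputation, and the last-visit sentence in 16.2.7, with a reference to 16.2.8. Keep the EOT/EOS visit in 16.2.8 as an upper cap. Replace its open-ended category with a named list drawn from dates already collected. State that this single derived date is used in both arms for treatment duration, PEY, TEAE status, the hospitalization window, transfusion time at risk and unit counts, and the Efficacy Emergent Period. Report the number of subjects with an imputed last-dose date by arm, so that the effect can be judged.

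The cost is SAP wording, one derived variable and one line in a disposition or exposure table. No new data are needed, provided the named dates are limited to those already on the eCRF.
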